Specific Aim 8: We will assess the direct and indirect costs incurred by the mother and her family, stratified by whether or not she has a surgical site infection, and describe the burden of these costs relative to the overall financial expenditures of the household.

SUBJECT SELECTION AND ENROLLMENT:

This study will follow patients who received cesarean-section surgery at KDH and reside in Kirehe District. KDH is a 145-bed facility operated by the Rwanda Ministry of Health (RMOH) and supported since 2005 by the medical non-profit organization Partners In Health (PIH). The hospital serves a catchment area of 364,000 people, primarily residing in rural, outlying villages. In preliminary work, we conducted a chart review that showed that 7.3% of obstetric surgical patients and 3.1% of non-obstetric surgical patients returned to the hospital with an SSI. Based on regional literature, we expect the true rate of SSI in patients receiving surgery KDH to be 10-20%.²²

Phase 1

Participants will be adult (≥ 18 years) patients receiving cesarean-section surgery at KDH over a seven-month enrollment window. All patients receiving a cesarean section (c-section) surgery at KDH who reside in Kirehe district will be eligible and will be invited to participate on post-operative day 2. We anticipate enrolling 525 post-operative c-section patients who received surgery at KDH during the seven-month period. Patients will be enrolled consecutively. We will include patients from Mahama Refugee Camp when collecting information about the hospitalization and outcomes. However, these patients will not be asked to return for follow-up.

Phase 2

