For consenting participants that are discharged prior to their 10-day post-operative screening, a study data collector will administer a simple self-report survey to collect basic patient demographic and socioeconomic characteristics on the day of discharge. They will be asked to return to the clinic for screening. In line with national policies, these participants will receive a voucher worth approximately US \$10, to compensate for travel and time, to return to the clinic. The voucher will be redeemed when the patient arrives to their assigned screening day. If a participant misses his assigned screening day, the participant will be contacted via his local community health worker.

Consenting patients that are not discharged prior to their 10-day post-operative screening will have demographic and socioeconomic data collected via self-report survey administered by the

study data collector as well as GPs and sCHW conducting the physical examination on the assigned screening day. These participants will not receive any voucher. Study staff will also extract clinical data from the patient files of all consenting participants.

[figure not shown]
We anticipate enrolling a minimum of 525 post-operative patients during the five-month period. With an estimated overall SSI rate of 15% based on existing literature and 10% loss-to-follow-up (LTFU), we expect 71 patients will have a GP-diagnosed SSI and 402 patients will not have a GP-diagnosed SSI.

PHASE 2:

After the screening protocol has been optimized in phase 1, new patients receiving c-section surgery at KDH will be enrolled and randomized to one of three study arms. Rates of return and severity of SSI at return across the three arms will be compared (Aim 4). We will also report process indicators to describe the implementation of the CHW-mHealth interventions (Aim 5). For patients that have contact with a sCHW (Arms 1 and 2), and are suspected to have a SSI and referred back to care but fail to return, we will assess their barriers to care (Aim 6). For patients that have no special follow-up, we will assess their post-operative follow-up practices (Aim 7). Embedded in this study will be a small sub-study on the costs of care and impact of these costs on family expenses (Aim 8).

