Patients in Arms 1 and 2, who are determined by the sCHW to have a suspected SSI and referred back to care, but fail to return back to care within one week will be identified. Data collectors will return to these patients' homes at 22-30 days post-operation to interview them on why they failed to return to care. The interviews will be semi-structured, including questions on established barriers to care and allowing for open-ended response. A random sample of patients in Arm 3 will be visited at home at 22-30 days post-operation by data collectors who will

interview them on their follow-up care procedures. The interviews will be semi-structured, including questions on standard care paths and allowing for open-ended response.

For a subset of 50 patients, we will administer at discharge a Financial Risk Protection Survey (Appendix D), an existing validated tool, to understand the total costs of care and the costs relative to normal household expenditures.

Analysis and Outcomes:

Aim 4:

For Aim 4, we will compare the proportion of patients who return for follow-up with an SSI in Arms 1 and 2 to Arm 3 (standard of care) using a two-sided, two-sample test of proportions at the $\alpha=0.05$ significance level. We will use a logistic regression model to assess the impact of study arm on measures of severity at presentation (for example, readmission to hospital), controlling for potential confounders collected at enrollment. All analyses will be completed as intention to treat, regardless of whether the patient had contact with the sCHW or was screened by the mHealth tool in Arms 1 and 2. For Aim 4, for Arms 1 and 2, we will report percent for each of the process measures (for example, percent of home visits or calls completed on time) with 95% confidence intervals. We will assess the impact of study arm on measures of severity at presentation, controlling for potential confounders collected at enrollment. We will describe standard of care patient follow-up behavior using results from Arm 3. We will also report surgery-related reasons for return to care beyond SSI. We will perform a sensitivity analysis to determine under what range of SSI rates the results are still valid.

Aim 5:

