For Aim 5, we will report percent for each of the process measures with 95% confidence intervals. Process measures include: ability to find the patient's home (Arm 1), willingness to allow sCHW into home (Arm 1), percent of home visits completed (Arm 1), successful use of GPS (Arm 1), availability of phone (Arm 2), availability of patient when called (Arm 2), visits or calls completed on-time (Arms 1 and 2), percent of reports successfully transmitted via the application (Arms 1 and 2) and presentation to care upon referral (Arms 1 and 2).

Aim 6:

For Aim 6, we will identify potential predictors for failure to return, comparing those who were recommended in Arms 1 and 2 to return and did return to those who failed to return using logistic regression. Demographic and clinical predictors collected at enrollment will be used as potential predictors. All factors significant at the $\alpha=0.2$ significance level in the bivariate analysis will be considered for the multivariate analysis. We will build the final predictive model using backward stepwise regression, stopping when all factors remain significant at the $\alpha=0.05$. For those that fail to return to care, we will report their barriers to care using proportions and 95% confidence intervals. Responses to open ended questions will be transcribed and translated, and we will identify any unaddressed themes using a general inductive approach.

Aim 7:

For Aim 7, we will evaluate patient post-operative care behaviors using proportions and 95% confidence intervals. Responses to open ended questions will be transcribed and translated, and we will identify any unaddressed themes using a general inductive approach.

Aim 8:

For Aim 8, we will describe the median and ranges of expenses incurred by patients, stratified by whether or not the patient had a surgical site infection. We will also describe the median and range for the normal household expenditures and compare the care expenses relative to normal household expenditures.

Power Analysis:

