The sample size for Phase 2 of this study was driven by Aim 4. We assume that the rates of SSI in the three arms will be similar (due to randomization), and we anticipate more patients with SSI will return to care in Arms 1 and 2 than in Arm 3. In each arm, we will enroll 364 patients. Assuming a 15% SSI rate, this translates to 55 SSI cases per arm. In Arm 3, we expect approximately 6% of all surgical patients to return with an SSI corresponding to 40% of all SSI infections. In Arms 1 and 2, we hypothesize twice as many patients with SSI (80%, n=44) will return. We would have an 81% power to detect a difference between the rate of patients that returned with SSI in Arms 1 and 2 (12%) as compared to Arm 3 (6%) with a two-sided test at the $\alpha=0.05$ significance level (Table 1).

	Arm 1	Arm 2	Arm 3
Description	Home visit on 10 th post-operative day (± 3 days)	Phone call on 10 th post-operative day (± 3 days)	Standard of care
Number per arm	364	364	364
Anticipated number with SSI	55	55	55
Hypothesized number to return with SSI days 7-14	44 (80%)	44 (80%)	22 (40%)
Overall hypothesized proportion that	0.12	0.12	0.06

will return on POD 7-14 with SSI			
--	--	--	--

RISKS AND DISCOMFORTS:

The study does not alter the standard of care in any way that increases risk to the patient. Risks to privacy are minimized by accessing data on password protected mobile phones, storing data on HIPAA-compliant servers, and de-identifying the database as soon as is practicable after the conclusion of the study period.

The primary risk associated with participation in this study is a breach in confidentiality, resulting in the disclosure of patient information. This risk is considered minimal; as unique codes will be used in place of participant names. All study staff will be trained in confidentiality. To further reduce the likelihood of a breach in confidentiality, all digital information will be stored in a password-protected document on an encrypted study computer, and all paper records will be stored in a locked file cabinet in a secure room at KDH.

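### Aim 8 splits costs by SSI status, but its 50 women are surveyed at discharge: about 5 known SSIs are expected, and the costs of a later return are not captured

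*Combined protocol and SAP*

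**What the plan says.** The Specific Aims section sets Aim 8 as the direct and indirect costs to the mother and family, split by SSI status and set against household spending. Analysis and Outcomes, Aim 8, repeats the split: "we will describe the median and ranges of expenses incurred by patients, stratified by whether or not the patient had a surgical site infection". Study Procedures, Phase 2, gives the scale: "Embedded in this study will be a small sub-study on the costs of care and impact of these costs on family expenses (Aim 8".

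The data source is in Biostatistical and Qualitative Analysis, Phase 2: "For a subset of 50 patients, we will administer at discharge a Financial Risk Protection Survey (Appendix D". No later cost survey is described, and how the 50 are chosen is not stated.

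The timings that bear on this are as follows.

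- Women are randomised at discharge, and those still in hospital at day 10 are excluded (Subject Selection and Enrollment, Phase 2).
- SSI symptoms usually appear on post-operative days 6-9 (Study Procedures).
- The surgical community health worker (sCHW) screen is at day 10 ± 3, in Arms 1 and 2 only. GP-recorded SSI status comes from Kirehe District Hospital (KDH) charts, alongside a log of women who return or self-present (Biostatistical and Qualitative Analysis, Phase 2).
- Data collectors interview two groups at home at days 22-30: referred women in Arms 1 and 2 who did not return, and a random sample of Arm 3. No wound assessment is described at these visits.

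The planning rates are in Power Analysis: "Assuming a 15% SSI rate, this translates to 55 SSI cases per arm"; "In Arms 1 and 2, we hypothesize twice as many patients with SSI (80%, n=44) will return"; and for Arm 3, "we expect approximately 6% of all surgical patients to return with an SSI corresponding to 40% of all SSI infections". Subject Selection and Enrollment gives a wider range, in percent: "we expect the true rate of SSI in patients receiving surgery KDH to be 10-20".

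The protocol does not say which source defines SSI status for Aim 8, or how a woman who does not return is classified.

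**The concern.** The split by SSI status is the substance of Aim 8, but the women are sampled and questioned at a point when that status is, for most, probably not yet settled. Three things follow.

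- The women cannot be selected on a later SSI, so the two groups form at whatever rate infections occur and are detected. With 50 women, the SSI group will be very small.
- Costs of a later return, readmission or reoperation have not been incurred at discharge and cannot be recorded there. Even a larger SSI group would largely lack the costs that set it apart.
- With no rule for non-returners, the content of the no-SSI group is undefined. The gap is widest in Arm 3, which has no screen.

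At stake is whether a stated aim can be answered. The Aim 4 analysis is not affected.

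**Working it through.** **1. The plan's own figures.** With 364 women per arm, 364 × 0.15 = 54.6, or 55 SSIs. Then 55 × 0.80 = 44 and 55 × 0.40 = 22; as shares of all women these are 44/364 = 12% and 22/364 = 6%. For power, pooled p = 0.09:

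- SE under no difference = √(2 × 0.09 × 0.91 / 364) = 0.02121
- SE under the alternative = √((0.12 × 0.88 + 0.06 × 0.94) / 364) = 0.02110
- z = (0.06 − 1.96 × 0.02121) / 0.02110 = 0.873, giving power 80.9%

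This matches the stated 81%, so the rates are internally consistent and can be carried into Aim 8. The protocol gives no figure for Aim 8 other than 50.

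**2. Expected known SSIs among 50.** Formula: 50 × SSI rate × share of SSIs that return. Assumptions: selection does not depend on SSI status, and a known SSI is one that returns. With an even spread over the arms the share is (0.80 + 0.80 + 0.40)/3 = 0.667. At 15%: 50 × 0.15 × 0.667 = 5.0.

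| SSI rate | True SSIs in 50 | Known, even spread | Known, all from Arms 1/2 | Known, all from Arm 3 | Unreturned, even spread |
|---|---|---|---|---|---|
| 10% | 5.0 | 3.3 | 4.0 | 2.0 | 1.7 |
| 15% | 7.5 | 5.0 | 6.0 | 3.0 | 2.5 |
| 20% | 10.0 | 6.7 | 8.0 | 4.0 | 3.3 |

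The expected count therefore lies between 2 and 8 whatever the arm mix.

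**3. Chance variation.** For Binomial(50, 0.10), the 2.5th to 97.5th percentiles are 1 to 9. P(2 or fewer) = 11%, P(3 or fewer) = 25%, P(10 or more) = 2.5%.

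**4. Unreturned SSIs, if they were placed in the no-SSI group.** At 15% with an even spread, 2.5 of 45 women, or 5.6%. Each arm contributes 50/3 × 0.15 = 2.5 true SSIs. Unreturned are 2.5 × 0.20 = 0.5 in each of Arms 1 and 2, and 2.5 × 0.60 = 1.5 in Arm 3. Arm 3 thus holds 1.5 of the 2.5.

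**5. Cases available.** Returning SSIs expected: 44 + 44 + 22 = 110, of which 88 are in Arms 1 and 2. As a low case, take 10% SSI and only the Arm 3 return share in both intervention arms: 728 × 0.10 × 0.40 = 29. Twenty-five cases from Arms 1 and 2 would still be expected.

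**The case against.** The strongest reply is that this is a small descriptive sub-study. The plan promises medians and ranges, with no test, no contrast between the groups and no power claim. A small SSI group is then a limit of choosing 50, not an error. This stands in part: it would be wrong to judge Aim 8 by the standard error of a difference that nobody plans to estimate. But the split is the aim itself, and a median and range from about 5 women, possibly 1 or 2, describes little.

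Several stronger readings are tempting, and the documents do not support them.

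- *Unreturned SSIs are counted as uninfected.* A reader might infer this, but no classification rule is given. They may be so counted; that is as far as the text goes. Even if they were, 5.6% of the group would hardly move its median, though it could move the range.
- *SSI status is known only from charts of women who return.* In Arms 1 and 2 the sCHW screen is also recorded, and referred women who fail to return are identified and visited. The gap is mainly in Arm 3.
- *No SSI can be known at discharge.* The usual day of discharge is not stated, and some infections may be evident by then. That most status is settled later is inferred from the timings above.
- *Survey timing by itself makes the group small.* The count comes from 50 and the rates. Timing matters because it rules out selecting on a later SSI.

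It is also fair that the selection of the 50 is unstated, so the figure of 5 rests on an assumed even spread. The range of 2 to 8 removes that dependence.

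**Conclusion.** The point holds, and the sponsor should act on it. As written, Aim 8 would probably rest on about 5 known SSIs (expected 2 to 8; binomial range 1 to 9 at the central assumptions), although about 110 women are expected to return with an SSI. The survey would also miss the costs of a later return or readmission, which may matter more than the count. The handling of non-returners is a gap in the plan, not a demonstrated misclassification.

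The figures rest on the plan's 15% SSI rate (10-20% as the range), its hypothesised return shares, selection unrelated to SSI status, and most SSIs becoming known after discharge.

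**What to change.** Keep 50 surveys and change when they are done and whom they cover.

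- In Biostatistical and Qualitative Analysis, Phase 2, move the survey from discharge to a point after SSI status is known.
- Take about 25 women charted with an SSI at KDH and about 25 who were screen-negative and not charted with an SSI. Draw both groups from Arms 1 and 2, so that arm is not mixed with SSI status, and choose both by the same method, random or consecutive.
- Use one post-operative cost window for both groups, for example by phone or visit at the existing day 22-30 data-collector time point, so that costs of a return have had time to accrue.
- In Analysis and Outcomes, Aim 8, state the source that defines SSI status. State that Arm 3 women of unknown status are not counted as uninfected, and say how referred non-returners and women the sCHW did not reach are handled.
- Report the two groups separately, and weight any pooled figure to the observed SSI proportion.

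The cost is more than a change of wording: up to about 50 later phone or home contacts by existing staff, in place of surveys at discharge. Three limits remain. The SSI group represents women who returned. The no-SSI group rests on an imperfect screen (Phase 1 accepts 90% sensitivity with in-person screening, whereas Arm 2 is screened by phone). Costs arising after the chosen window are not counted.

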We will continue to consecutively enroll participants on post-operative day 2 from the adult female patient population receiving c-section surgery at KDH during a 14-month period. Randomization into the three study arms will take place at time of discharge. We will enroll 1092 participants in this phase of the study, 364 per study arm. Once enrolled, there will be no special retention strategies so as not to interfere with the outcomes under investigation in Aim 4 (return to care) or Aim 5 (process measures describing the CHW-mHealth intervention implementation). If the patient is still in the hospital 10 days following surgery, they will be excluded from the study given the inability to be randomized properly to the three arms of this phase. We will include patients from Mahama Refugee Camp when collecting information about the hospitalization and outcomes. However, these patients will not be asked to return for follow-up.

Sealed study packets, prepared in advance, will be available at KDH. Each study packet will have the arm assignment for the patient, which will be randomly assigned during the preparation of the materials using a random number generator. Both the research staff and the patient will be unaware of the arm assignment during the consent process and the assignment will be revealed only after the patient has agreed to participate. In this phase, no participants will receive travel vouchers, to ensure appropriate comparison between the intervention and standard of care groups. Per standard of care, all patients will receive information on the signs of SSI and will be instructed to return as soon as any of these present. (Appendix A).

STUDY PROCEDURES:

This research includes two distinct phases. During the first phase, we will optimize the SSI screening protocol by piloting it among a cross-section of patients receiving surgery at KDH, Rwanda. In the second phase, we will randomize patients receiving surgery at KDH to one of three arms – standard of care and the two intervention arms. At the conclusion of the study, we will compare rates of return and severity of SSI at return among the three arms and report process indicators describing the implementation of the CHW-mHealth interventions in the two intervention arms. In this study, patients will be assessed at 10 days after their operation, as symptoms for SSI usually develop during the first 6-9 post-operative days.²³

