All consenting participants will have basic demographic and socioeconomic data collected by self-report via a survey administered by the study data collector at time of discharge. The study data collector will extract additional clinical data from the patient file. At time of discharge, participants will receive surgery follow-up instructions (Appendix A), including a set of warning signs for SSI and when to return to a health center, per standard of care. Additional human subjects contact will depend on study arm assignment. Individuals in Arm 1 will be visited at home by the sCHW who will administer the optimized SSI protocol via the mHealth device. Following the screening, the sCHWs will use the cell phone to photograph the surgical wound and record the GPS location of the visit. Individuals in Arm 2 will be phoned by the sCHW who will administer the SSI protocol over the phone. Individuals in Arm 3 will not have any additional contact beyond standard of care (Figure 1).

Figure 1:

BIOSTATISTICAL AND QUALITATIVE ANALYSIS:

Phase 1:

At the time of enrollment, study staff will administer a basic survey to record self-reported data on patient demographics (gender, age, weight, height, education level, location of residence, distance to hospital) and socioeconomic status (monthly household income, land ownership, cost of transport as a barrier to receiving health care). Study staff will also extract data from clinical charts on past medical history, type of surgery, time from surgery recommendation to operation, pre-operative antibiotic use/time, wound class, and any documented surgical complications. Clinical information will continue to be collected up to 90 days for any patients who are never discharged or for any patient who is readmitted for a surgical complication. For patients that are transferred to Kigali for tertiary care, we will use data collected routinely collected by the Right to Health Care program to complete their follow up information.

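### The Aim 4 comparison of return with SSI is unadjusted although useful baseline variables are already collected in every arm; adjusting it is a nearly free but modest improvement

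*Combined protocol and SAP*

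**What the plan says.** Under Analysis and Outcomes, Aim 4 (Phase 2), the proportion returning with an SSI in Arms 1 and 2 is compared with Arm 3 "using a two-sided, two-sample test of proportions". No covariates are named. The next sentence plans a logistic model, but for severity at presentation, "controlling for potential confounders collected at enrollment". The only sensitivity analysis for Aim 4 varies the SSI rate. No adjusted analysis of return with SSI is described.

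The Power Analysis section says that Aim 4 set the Phase 2 sample size: "We would have an 81% power to detect a difference" between 12% and 6%, "with a two-sided test at the $\alpha=0.05$ significance level". Subject Selection and Enrollment, Phase 2, gives the size: "We will enroll 1092 participants in this phase of the study, 364 per study arm". Assignment there comes from a random number generator, with no stratification or blocking stated.

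The Phase 1 part of the Biostatistical and Qualitative Analysis section lists the variables to be recorded. They include weight, height, "distance to hospital) and socioeconomic status (monthly household income, land ownership, cost of transport as a barrier to receiving health care", and, from the chart, wound class and documented surgical complications. The Phase 2 part carries this baseline collection over, and Study Procedures, Phase 2, applies the survey and the chart extraction to all consenting participants.

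**The concern.** The outcome has two parts: a woman must have an SSI, and she must travel back to the hospital. The protocol's Background names geographic and financial barriers as reasons for not returning, and its Potential Benefits section calls transport cost a known barrier. Phase 2 gives no travel support, so these barriers remain. Variables that plausibly predict the outcome are therefore available in all three arms. They are used for severity but not for the outcome that determines the sample size.

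Two things are at stake: some precision, and protection against chance imbalance that simple randomisation does not prevent. A third is discipline. The set of potential confounders for the severity model is not listed, so an adjusted analysis of return added later would involve choosing covariates after seeing the data.

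**Working it through.** **Inputs from the documents.** 364 women per arm; 12% v 6%; two-sided alpha 0.05; stated power 81%; 44 v 22 expected returns with SSI (80% and 40% of 55 cases), so 66 events per pairwise comparison. The documents give no prognostic strength for any covariate. Every R² and c-statistic below is an assumption.

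**1. The plan's own figure.** The mean proportion is 0.09.
- Null SE = √(2 × 0.09 × 0.91 / 364) = 0.02121.
- Alternative SE = √((0.12 × 0.88 + 0.06 × 0.94) / 364) = 0.02110.
- Power = Φ((0.06 − 1.96 × 0.02121) / 0.02110) = Φ(0.873) = 80.9%.

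The stated 81% is therefore an unadjusted comparison of one intervention arm with Arm 3. Pooling Arms 1 and 2 (728 v 364) would give 90.1%.

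**2. Gain by formula.** Multiplying both variances by (1 − R²) gives power = Φ((0.06 / √(1 − R²) − 1.96 × 0.02121) / 0.02110). The equivalent unadjusted size is 364 / (1 − R²).

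| Assumed R² | Power | Equivalent n per arm |
|---|---|---|
| 0 | 80.9% | 364 |
| 0.01 | 81.3% | 368 |
| 0.02 | 81.7% | 371 |
| 0.03 | 82.0% | 375 |
| 0.05 | 82.8% | 383 |
| 0.10 | 84.8% | 404 |

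**3. Gain by simulation.** 4,000 trials per row, 364 v 364, with one prognostic score plus four uninformative covariates, so that the cost of estimating extra coefficients is included. The Monte Carlo error of each power is √(0.82 × 0.18 / 4000), about 0.6 points.

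| c-statistic of score (R²) | Unadjusted | Logistic Wald | Standardised risk difference |
|---|---|---|---|
| none | 81.9% | 81.1% | 81.7% |
| 0.61 (0.013) | 81.3% | 81.8% | 82.2% |
| 0.69 (0.042) | 82.0% | 83.4% | 83.8% |
| 0.75 (0.086) | 82.1% | 83.9% | 84.4% |
| 0.80 (0.14) | 81.7% | 86.3% | 86.9% |

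A separate simulation with three uninformative covariates gave gains for the standardised risk difference of about 0.5 to 1.5 points for modest to moderate prognostic strength and about 3.5 points for strong. Under no effect (3,000 trials per setting, Monte Carlo error about 0.4 points), the unadjusted test rejected in 4.4% to 5.6% of trials and the standardised risk difference in 4.3% to 6.0%.

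**4. Chance imbalance, on average.** In 2,500 trials per setting at 12% v 6%, with a single score, about 15% had the score unbalanced against the intervention by at least one SD of its chance distribution. In those trials (Monte Carlo error about 2 points):

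| c-statistic | Unadjusted power | Adjusted power |
|---|---|---|
| 0.65 | 72% | 80% |
| 0.71 | 74% | 84% |
| 0.76 | 71% | 85% |

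With imbalance favouring the intervention, unadjusted power rose to 86–93% and adjusted power stayed at 79–84%. Over all trials, the two analyses disagreed on significance in 4–7%.

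**5. Chance imbalance, at the hypothesised result.** For 44 v 22 of 364 the pooled proportion is 66/728 = 0.0907, z = 2.84 and p = 0.0045. Significance is lost at 36 v 22 (p = 0.055), a shift of eight events. Now assume a binary distance factor present in 30–50% of women, with an odds ratio for return of 0.5 or 0.33. A two-SD unfavourable imbalance, about 7 percentage points, moves p only to 0.007–0.011.

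**The case against.** The strongest reply is that nothing here is an error. A two-sample test of proportions is valid in a randomised trial and matches the power calculation. That stands in full. A reader might infer from the missing adjustment that the planned test is biased or has the wrong error rate; neither the documents nor the simulations support that.

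A reader might also infer that a modest imbalance could overturn the hypothesised 44 v 22 result. Step 5 shows that it would not. Imbalance changes the conclusion mainly when the result is already near 0.05.

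Nor is adjustment a gain in every case. The size rests on assumed prognostic strength. With uninformative covariates the gain is nil, and the logistic Wald test was slightly lower (81.1% v 81.9%).

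Two practical objections also stand and shape the fix:
- Documented surgical complications are not secured as pre-assignment data. Data Safety, item 2, allows chart extraction after the return visit, and clinical collection runs to 90 days for women readmitted with a surgical complication. An SSI may itself be such a complication, so adjusting for this variable could mean adjusting for the outcome.
- Missing covariates could cancel the benefit. At R² of 0.02–0.03 the gain is worth 371 − 364 = 7 to 375 − 364 = 11 women per arm, about 2–3%. A complete-case model losing that share would gain nothing and would breach the stated intention-to-treat principle.

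**Conclusion.** The point holds as a modest improvement to efficiency and robustness, not as a correction of a faulty test. The main comparison is unadjusted, plausible predictors are planned for collection in all arms, no stratification is stated, and the plan already accepts adjustment for severity. Expected benefit is roughly 0.5 to 4 power points over most of the assumed range. It is about 5 points only if the covariates reach a c-statistic near 0.80, and zero if they predict nothing. Protection against imbalance is the more useful part in an unlucky allocation, but it decides the conclusion only in borderline results. These sizes assume the planned 12% v 6%, 364 per arm, and covariates measured before assignment is known.

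**What to change.** In Analysis and Outcomes, Aim 4, before any comparison by arm (including the seven-month interim analysis):

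- Make the main analysis of return with SSI a logistic model with arm and a short list fixed in advance: distance to hospital, transport cost as a barrier, body mass index from weight and height, and wound class if it varies among these caesarean patients. With 66 events per comparison, the list should stay short.
- State that these covariates are recorded before assignment is revealed. The text needs to be explicit because the Phase 2 survey is placed at discharge in Study Procedures and at enrollment in Data Safety, while randomisation is at discharge. Exclude complications documented or extracted after assignment.
- Report a standardised risk difference with 95% CI for each intervention arm v Arm 3, naming the variance estimator.
- Handle missing covariates by simple imputation or a missing indicator, so that no randomised woman is dropped.
- Keep the unadjusted test of proportions as supportive.

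The cost is analysis wording, a missing-covariate rule and attention to the timing of baseline recording. No additional patients or variables are needed.
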